12.3.2. Calculated Parameters

The QTc will always be derived during the statistical analysis, even when already available in the database. The value in the database will not be used in the analysis.

The QTc will be calculated using the following formula: Fridericia's cube-root corrected QT (Fridericia, 1920):

$$QTcF \text{ (ms)} = QT \text{ (ms)} \times \sqrt[3]{\frac{HR(bpm)}{60}}$$

The QTcF will be rounded up to the nearest integer prior to the derivation of changes and categorizations.

12.3.3. Baseline and Change from Baseline

The baseline is defined as the last nonmissing value prior to dosing. Baseline will be determined per ECG parameter individually. It is recognized that baseline parameters may thus come from more than one ECG reading and not just from the "baseline visit" reading.

The change from baseline will be calculated for all post-baseline time points as:

Change from baseline at time point t = value at time point t – baseline value.

12.3.4. Visits for analysis

An ECG is only taken at Screening (baseline), Week 12, Week 24/EDV and Follow-up. Therefore the analysis will not use any time windowing, but will just present the visits as they are: Baseline, Week 12 and Week 24, and Follow-up. See also mocks.

In case the subject prematurely discontinues the study during the first period of the study, the EDV ECG will be used as “Week 12”. In case the subject prematurely discontinues the study during the second period of the study, the EDV ECG will be used as “Week 24”.

Because of this, there will not be a “last on-treatment” nor a “worst-case”.

12.3.5. Normal Ranges

For the QT and QTcF parameters, the following categorizations will be done:

- of the actual values:
 - ≤ 450 ms,
 -]450,480] ms,
 -]480,500] ms,
 - >500 ms;
- of the changes from baseline:
 - ≤ 30 ms (including all decreases in QT),
 -]30,60] ms,
 - >60 ms.

12.3.6. Analysis tables at Week 12

No formal inferential statistics (p-values) are planned in this SAP.

If the subject did not participate in the second period of the study, then the follow-up visit will be presented in the table of the first period of the study. If the subject participated in the second period of the study, then the follow-up value will be presented in the table of the second period of the study, not of the first period.

Table 14.3.3.1: ECG up to Week 12: Descriptive statistics of the actual values per time point

Descriptive statistics of the actual values per test and unit, and per treatment group.

Population: safety.

Table 14.3.3.2: ECG at Week 12: Descriptive statistics of the changes from baseline

Descriptive statistics of the changes from baseline (including 95% confidence interval of the mean change) per test and unit, and per treatment group. The actual value at baseline will also be presented in this table.

Population: safety.

Table 14.3.3.3: ECG at Week 12: Shift table of the QT abnormalities

Shift table per test, treatment group and time point. The table will present the shift in abnormality at each post-baseline time point (including the worst-case) versus the baseline abnormality. Parameters: QT and QTcF.

Population: safety.

Table 14.3.3.4: ECG at Week 12: Treatment-emergent QT abnormalities

Frequency table of the treatment-emergent abnormalities per parameter and treatment group. A post-baseline abnormality is considered treatment-emergent if it is higher than the baseline result. Parameters: QT and QTcF.

Population: safety.

Table 14.3.3.5: ECG at Week 12: Treatment-emergent abnormal change in QT

Frequency table per test and treatment group. The table will present the abnormality of the changes. Parameters: QT and QTcF.

Population: safety.

Table 14.3.3.6: ECG up to Week 12: Frequency table of the eCRF ECG interpretation per time point

Frequency table per treatment group of the ECG interpretation scores as recorded in the eCRF. Interpretation scores are:

- Normal ECG in sinus rhythm;
- Cardiac conduction disorders;
- Rate and rhythm disorders;
- Supraventricular arrhythmias;
- Ventricular arrhythmias.

Note that more than one of these items can be ticked.

Population: safety.

12.3.7. Analysis tables for the whole 24 weeks period

Repeat tables, population=safety, with the adapted treatment groups focusing on subjects who used GLPG0634 during both study periods:

Table 14.3.3.7: ECG over the whole study: Descriptive statistics of the actual values per time point**Table 14.3.3.8: ECG over the whole study: Descriptive statistics of the changes from baseline****Table 14.3.3.9: ECG over the whole study: Shift table of the QT abnormalities****Table 14.3.3.10: ECG over the whole study: Treatment-emergent QT abnormalities****Table 14.3.3.11: ECG over the whole study: Treatment-emergent abnormal change in QT****Table 14.3.3.12: ECG over the whole study: Frequency table of the eCRF ECG interpretation per time point**

12.3.8. Figures

No figures planned.

12.3.9. Listings

Listing 16.2.12.1: ECG: Full listing

Listing per treatment group, per subject and per time point of the ECG parameters (raw values as well as changes from baseline), flagging abnormal results. Includes the ECG interpretation and morphology findings.

Population: safety.

Listing 16.2.12.2: ECG: Abnormalities listing

Listing per treatment group, per subject and per time point of all data scored as out-of-normal-range or clinically significant, plus also the baseline reference time point.

Population: safety.

12.4. VITAL SIGNS

12.4.1. Available Data

Available parameters: pulse rate, diastolic and systolic blood pressure, temperature.

12.4.2. Baseline and Change from Baseline

The baseline value will be the last nonmissing value prior to first dosing. Baseline will be determined per vital signs parameter individually. It is recognized that baseline parameters may thus come from more than one vital signs reading and not just from the “baseline visit” reading.

The change from baseline will be calculated for all post-baseline time points as:

Change from baseline at time point t = value at time point t – baseline value.

12.4.3. Normal Ranges

Parameter, unit	Normal range	
	Lower limit	Upper limit
Pulse, bpm	40	100
DBP, mmHg	45	90
SBP, mmHg	90	140
Temperature, °C	35.5	37.5

Values equal to the boundaries are still considered normal (N). A value is classified as abnormally low (L) when the value < lower limit of the normal range. A value is classified as abnormally high (H) when the value > upper limit of the normal range.

12.4.4. Last on-treatment result

Derived per parameter separately, for values as well as abnormalities.

Three last on-treatment determinations will be done, depending on the chapter of analysis:

1. Including all nonmissing post-baseline values, including “use=No” and unscheduled measurements, up to and including the Week 12 value.
2. Including all nonmissing post-Week 12 values, including “use=No” and unscheduled measurements, up to and including the Week 24 value.
3. Including all nonmissing post-baseline values, including “use=No” and unscheduled measurements, up to and including the Week 24 value.

Early discontinuation visits are considered as on-treatment visits as well.

12.4.5. Worst-Case Abnormality

Derived per parameter separately, for abnormalities only.

Three worst-case determinations will be done, depending on the chapter of analysis:

1. Including all nonmissing post-baseline values, including “use=No” and unscheduled measurements, up to and including the Week 12 value. Also including the follow-up value in case the subject did not participate in the second period of the study. If the subject participated in the second period of the study, then the follow-up value will be included in the worst-case of the second period of the study, not of the first period.
2. Including all nonmissing post-Week 12 values, including “use=No” and unscheduled measurements, up to and including the follow-up value.
3. Including all nonmissing post-baseline values, including “use=No” and unscheduled measurements, up to and including the follow-up value.

Possible categories:

- H = abnormally high: at least one postdose measurement is above the normal range, and there are no values below the normal range.

- L = abnormally low: at least one postdose measurement is below the normal range, and there are no values above the normal range.
- H+L = abnormally high and low: at least one postdose measurement is above the normal range, and at least one other postdose measurement is below the normal range.
- N = normal: all postdose measurements are within normal limits.

12.4.6. Tables up to Week 12

No formal inferential statistics (p-values) will be derived. Time points to present: screening, baseline, Weeks 1-2-4-8-12, last on-treatment, worst case.

If the subject did not participate in the second period of the study, then the follow-up visit will be presented in the table of the first period of the study. If the subject participated in the second period of the study, then the follow-up value will be presented in the table of the second period of the study, not of the first period.

Table 14.3.4.1: Vital signs up to Week 12: Descriptive statistics of the actual values

Descriptive statistics of the actual values per test and unit, treatment group and time point.

Population: safety.

Table 14.3.4.2: Vital signs up to Week 12: Descriptive statistics of the changes from baseline

Descriptive statistics of the changes from baseline (including 95% confidence interval of the mean change) per test and unit, treatment group and time point. The actual value at baseline will also be presented in this table.

Population: safety.

Table 14.3.4.3: Vital signs up to Week 12: Summary table of means

Summary table per test and unit, treatment group and time point, showing only the mean value of actual values and changes from baseline.

Population: safety.

Table to be created for the Week 12 interim analysis as well.

Table 14.3.4.4: Vital signs up to Week 12: Shift table of the abnormalities per time point

Shift table per test, treatment group and time point. The table will present the shift in abnormality (L/N/...) at each post-baseline time point (including the worst-case) versus the baseline abnormality (L/N/H).

Population: safety.

Table 14.3.4.5: Vital signs up to Week 12: Treatment-emergent abnormalities per time point

Frequency table of the treatment-emergent abnormalities per parameter, treatment group and time point (including the worst-case). A post-baseline abnormality is considered treatment-emergent if it is different from the baseline result.

Population: safety.

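### Vital-signs tables cannot count a further rise in a parameter already above range at baseline, and no graded or change-class table stands behind them

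*SAP*

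**What the plan says.** SAP 12.4.3 gives one normal range per vital sign: pulse 40–100 bpm, diastolic pressure 45–90 mmHg, systolic pressure 90–140 mmHg, temperature 35.5–37.5 °C. There is a single open-ended class on each side: "A value is classified as abnormally high (H) when the value > upper limit of the normal range". A value on the limit is normal. For the reference value, SAP 12.4.2 says: "The baseline value will be the last nonmissing value prior to first dosing".

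Table 14.3.4.5 (SAP 12.4.6) is the frequency table of treatment-emergent abnormalities, and its rule is: "A post-baseline abnormality is considered treatment-emergent if it is different from the baseline result". Table 14.3.4.10 repeats it for the 24 weeks. Shift Tables 14.3.4.4 and 14.3.4.9 use the same classes. The worst-case determination in SAP 12.4.5 adds one class: "H+L = abnormally high and low: at least one postdose measurement is above the normal range", together with at least one other below it.

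For QT and QTcF, SAP 12.3.5 has four level classes and three change classes (cut-offs 30 and 60 ms). Table 14.3.3.4 uses a directional rule: "A post-baseline abnormality is considered treatment-emergent if it is higher than the baseline result". Table 14.3.3.5 tabulates the change classes.

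**The concern.** A table headed treatment-emergent abnormalities is where a reader looks to see how many subjects per arm got worse. For a subject who starts above the limit, this table cannot register a rise of any size in that parameter. It does count a 2 mmHg drift across the limit. The protocol's eligibility criteria set no blood pressure limit, so such subjects can enter.

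Safety and tolerability compared with placebo is a secondary objective. Subjects with a high baseline are the ones most likely to reach high absolute values, and no vital-signs table gives their worsening as a count by arm.

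**Working it through.** The plan states no figure for this rule, so there is none to reproduce. The check applies the rule to every class pair and then sizes the gap under stated assumptions.

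**1. Class pairs.** A pair counts as treatment-emergent if the post-baseline class is abnormal and differs from the baseline class.

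| Baseline | Post L | Post N | Post H | Worst case H+L |
|---|---|---|---|---|
| L | no | no | yes | yes |
| N | yes | no | yes | yes |
| H | yes | no | **no** | yes |

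A baseline-H subject is counted only through a low reading. Systolic 145 followed by 88 gives L. Systolic 145 followed by 190 and 88 gives a worst case of H+L.

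**2. Examples from the SAP limits.**
- Not counted: systolic 141 to 200, systolic 145 to 190, diastolic 91 to 120.
- Counted: systolic 139 to 141, diastolic 88 to 91.

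Over all integer baselines of 141–220 systolic (post-baseline up to 260) and 91–140 diastolic (up to 180), no value at or above baseline is ever counted. The low side mirrors this, since L to L is not counted either. Reading the baseline result as the number rather than the class does not rescue the rule: almost every repeat abnormal reading would then be treatment-emergent.

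**3. What stands behind the same convention elsewhere in the SAP.**

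| Data | L/N/H or level classes | Graded or directional rule | Change classes |
|---|---|---|---|
| QT, QTcF | four levels | yes, higher than baseline | yes |
| CTCAE-graded laboratory tests | yes | yes, higher grade | no |
| ATP III lipids | yes | yes, higher category | no |
| Other laboratory tests (Table 14.3.2.5) | yes | no | only for inhibin B and testosterone |
| Vital signs | yes | no | no |

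**4. Subjects affected.** The documents give no blood pressure data. With the planned 70 per arm (protocol 8.8.2), if 10%, 20%, 30% or 40% are high at baseline, then 7, 14, 21 or 28 subjects cannot be counted for a rise in that parameter. No rule removes them from the denominator.

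**5. Size of the gap, by simulation.** All inputs are assumptions:
- true systolic pressure normal, with mean/SD 125/13, 128/14 or 132/15;
- within-subject SD 8 or 10;
- five post-baseline visits;
- drug effect 0 or +5 mmHg;
- 400,000 subjects per scenario.

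Results across the scenarios:
- Baseline above 140: 16–33% of subjects.
- Rise of at least 20 mmHg to a maximum above 160: 0.9–12% of subjects. In an arm of 70 that is 0.009 × 70 ≈ 0.6 to 0.12 × 70 ≈ 8.4 subjects.
- Share of that group that started above 140, and so is not counted: 38–62%. Pairing the extremes gives outer bounds of 0.38 × 0.6 ≈ 0.2 to 0.62 × 8.4 ≈ 5.2 subjects per arm.

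**6. Does the rule hide a drug effect?** With a +5 mmHg effect, the proportion in range at baseline and above 140 at worst case differs between drug and placebo by 10–12 percentage points. The proportion rising at least 20 mmHg to above 160 differs by 2–6 points.

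**The case against.** The case for leaving the tables alone is substantial.

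- **It is the prespecified convention.** Protocol 8.8.1.4 calls for low/normal/high categories and shift tables to determine treatment-emergent abnormalities, and SAP 6.1.3 repeats this. Normal-range laboratory Table 14.3.2.5 uses the same differs-from-baseline rule, and SAP 12.2.5 grades only selected tests. This stands: there is no contradiction or error against the protocol, and it would be wrong to infer that the SAP avoids the problem everywhere except in vital signs.
- **Worsening is visible elsewhere.** The protocol's adverse event definition covers aggravation of a condition already present at consent, and these events are tabulated by arm, preferred term and intensity. Change from baseline is summarised at each visit with median, extremes and a 95% interval for the mean. Listing 16.2.13.2 sets out-of-range values beside the baseline. This stands, with limits: adverse event reporting depends on investigator judgement, summary statistics do not count subjects, and listings do not compare arms. At the Week 12 interim, the only vital-signs table marked for production is the table of means.
- **The sizing selects on the outcome.** Requiring a maximum above 160 favours high baselines. Under the same assumptions, only 4–16% of all subjects rising at least 20 mmHg started above 140, or 7–22% of those who also end above 140. This stands, and the percentage in the working applies only to large rises to high absolute values.
- **A pressor signal would not be lost.** A reader might infer that the dose-versus-placebo contrast is understated. Step 6 does not support that: a group-level shift separates the arms more under the existing rule than under the large-rise count.

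**Conclusion.** The limitation is certain from the text. In Tables 14.3.4.5 and 14.3.4.10, a parameter above range at the last pre-dose reading cannot become treatment-emergent by rising, and the shift tables show it as high to high. Unlike QT, the CTCAE-graded tests and the ATP III lipids, vital signs have no finer table to fall back on.

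A reader might go further and say that a hypertensive subject is never counted. The documents do not support that. The rule works parameter by parameter, so a subject high on systolic pressure alone can still be counted on diastolic. A treated subject within range at baseline is normal and can be counted. The gap is confined to these frequency and shift tables.

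The loss is the per-arm count of subjects with large rises from a high baseline. The percentages rest wholly on assumed systolic distributions. These are descriptive safety tables without p-values, and the primary analysis is untouched. It is a cheap improvement of minor severity.

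**What to change.** Keep the L/N/H rows as they are. For systolic pressure, diastolic pressure and pulse, add one or both of the following:

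1. Change-from-baseline categories by arm, on the model of Table 14.3.3.5.
2. Ordered reporting bands beyond each limit, counting a post-baseline value as worsened when its band lies further from normal than the baseline band. This covers the low side too.

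Apply the bands to Tables 14.3.4.4, 14.3.4.5, 14.3.4.9 and 14.3.4.10. The sponsor should set the cut-offs, as reporting categories only, and record them in the SAP before unblinding for the final analysis.

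The cost is SAP wording and a few table rows from data already collected. The downside is longer tables, and any cut-offs will be conventional.

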12.4.7. Tables over the whole 24 weeks period

The same tables again, but with adapted treatment groups focusing on the subjects who used GLPG0634 during both study periods. Time points to present: screening, baseline, Week 1-2-4-8-12, last on-treatment during period 1, worst case during period 1, Weeks 16-20-24, last on-treatment during period 2, last on-treatment during the whole study, follow-up (all follow-up visits in the study), worst case during period 2, worst case during the whole study.

Population: Safety.

Table 14.3.4.6: Vital signs over the whole study: Descriptive statistics of the actual values

Table 14.3.4.7: Vital signs over the whole study: Descriptive statistics of the changes from baseline

Table 14.3.4.8: Vital signs over the whole study: Summary table of means

Table 14.3.4.9: Vital signs over the whole study: Shift table of the abnormalities per time point

Table 14.3.4.10: Vital signs over the whole study: Treatment-emergent abnormalities per time point

12.4.8. Figures

No figures are planned.

12.4.9. Listings

Listing 16.2.13.1: Vital signs: Full listing

Listing per treatment, per subject and per time point of all parameters: raw values, changes from baseline, and flagging abnormal results.

Population: safety.

Listing 16.2.13.2: Vital signs: Abnormalities listing

Listing per treatment group, per subject and per time point of all data scored as out-of-normal-range or clinically significant, plus also the baseline reference time point.

Population: safety.

12.5. PHYSICAL EXAMINATIONS

Listing 16.2.14.1: Physical examinations: Abnormal findings

Listing per treatment group, per subject and per time point of the selection of all abnormal findings.

Population: safety.

